14.1 Subject Disposition, Demographic, Baseline, and Other Summary Tables

Table 14.1.1
Summary of Subject Disposition
All Subjects Screened

	Imsidolimab	Placebo	All Subjects
Screened, n			xx
Randomized, n	xx	xx	xx
Not Treated, n (%) [a]	xx (xxx.x)	xx (xxx.x)	xx (xxx.x)
Treated, n (%) [a]	xx (xxx.x)	xx (xxx.x)	xx (xxx.x)
Completed placebo-controlled period, n (%) [b]	xx (xxx.x)	xx (xxx.x)	xx (xxx.x)
Completed open-label extension period, n (%) [b]	xx (xxx.x)	xx (xxx.x)	xx (xxx.x)
Completed the Study including follow-up, n (%) [b]	xx (xxx.x)	xx (xxx.x)	xx (xxx.x)
Discontinued from Study Treatment, n (%) [b]	xx (xxx.x)	xx (xxx.x)	xx (xxx.x)
Early Discontinuation from Study, n (%) [b]			
Reasons for Discontinuation			
Any significant AE, laboratory abnormality, or other medical condition or situation occurs, such that continued participation in the study would not be in the best interest of the subject, in the opinion of the Investigator, n (%) [c]	xx (xxx.x)	xx (xxx.x)	xx (xxx.x)
Disease progression which requires discontinuation of the study treatment, n (%) [c]	xx (xxx.x)	xx (xxx.x)	xx (xxx.x)
Withdrawal of consent, n (%) [c]	xx (xxx.x)	xx (xxx.x)	xx (xxx.x)
Withdrew consent due to possible/perceived lack of efficacy by subject, n (%) [c]	xx (xxx.x)	xx (xxx.x)	xx (xxx.x)
Withdrew consent due to AEs experienced, n (%) [c]	xx (xxx.x)	xx (xxx.x)	xx (xxx.x)
Administrative reasons/Other, n (%) [c]	xx (xxx.x)	xx (xxx.x)	xx (xxx.x)
Termination of the subject participation by the Investigator or Sponsor, n (%) [c]	xx (xxx.x)	xx (xxx.x)	xx (xxx.x)
Use of any prohibited medication or treatment that in the opinion of the Investigator necessitates the subject being withdrawn, n (%) [c]	xx (xxx.x)	xx (xxx.x)	xx (xxx.x)
Significant deviation/lack of compliance with protocol, n (%) [c]	xx (xxx.x)	xx (xxx.x)	xx (xxx.x)
Lost to follow-up, n (%) [c]	xx (xxx.x)	xx (xxx.x)	xx (xxx.x)
Pregnancy, n (%) [c]	xx (xxx.x)	xx (xxx.x)	xx (xxx.x)
Other, n (%) [c]	xx (xxx.x)	xx (xxx.x)	xx (xxx.x)

[a] The denominator for the percentages uses the number of subjects who were randomized.

[b] The denominator for the percentages uses the number of subjects who were randomized and treated.

[c] The denominator for the percentages uses the number of subjects who discontinued early from study.

Source: Listing x.x.

Report Generated by Program: <study>/<analysis>/statout/xxxx.sas

Version

YYYY-MM-DD hh:mm

DocUUID 5f304d69-fa51-4f4c-b33f-c61c50388239

*Notes to Programmer: Patients who completed placebo-controlled period is defined as patients who have completed predose safety/efficacy assessment at Week 16
Patients who discontinued from study treatment includes 1) those who early discontinued from study, and 2) those who did not receive all doses through Week 28*

Table 14.1.2
Summary of Demographics
ITT Analysis Set

Parameter	Imsidolimab (N=xx)	Placebo (N=xx)	All Subjects (N=xx)
Age at Baseline (Years) [a]			
n	xx	xx	xx
Mean	xxx.x	xx.x	xx.x
SD	xxx.xx	xx.xx	xx.xx
Median	xx.x	xx.x	xx.x
Q1, Q3	xx.x, xxx.x	xx.x, xx.x	xx.x, xx.x
Min, Max	xx, xx	xx, xx	xx, xx
Age Group at Baseline, n (%)			
[12, 18) years	xx (xxx.x)	xx (xxx.x)	xx (xxx.x)
[18, 65) years	xx (xxx.x)	xx (xxx.x)	xx (xxx.x)
[65, 75] years	xx (xxx.x)	xx (xxx.x)	xx (xxx.x)
Missing	x (xxx.x)	x (xxx.x)	x (xxx.x)
[12, 16) years	xx (xxx.x)	xx (xxx.x)	xx (xxx.x)
>= 16 years	xx (xxx.x)	xx (xxx.x)	xx (xxx.x)
Missing	x (xxx.x)	x (xxx.x)	x (xxx.x)
[12, 15) years	xx (xxx.x)	xx (xxx.x)	xx (xxx.x)
>= 15 years	xx (xxx.x)	xx (xxx.x)	xx (xxx.x)
Missing	x (xxx.x)	x (xxx.x)	x (xxx.x)
Sex, n (%)			
Male	xx (xxx.x)	xx (xxx.x)	xx (xxx.x)
Female	xx (xxx.x)	xx (xxx.x)	xx (xxx.x)
Missing	x (xxx.x)	x (xxx.x)	x (xxx.x)
Race, n (%) [a]			
Black or African American	xx (xxx.x)	xx (xxx.x)	xx (xxx.x)
White	xx (xxx.x)	xx (xxx.x)	xx (xxx.x)
Native Hawaiian or Pacific Islander	xx (xxx.x)	xx (xxx.x)	xx (xxx.x)
American Indian or Alaska Native	xx (xxx.x)	xx (xxx.x)	xx (xxx.x)
Asian	xx (xxx.x)	xx (xxx.x)	xx (xxx.x)
Other	xx (xxx.x)	xx (xxx.x)	xx (xxx.x)
Missing	xx (xxx.x)	xx (xxx.x)	xx (xxx.x)

Parameter	Imsidolimab (N=xx)	Placebo (N=xx)	All Subjects (N=xx)
Ethnicity, n (%)			
Hispanic or Latino	xx (xx.x)	xx (xx.x)	xx (xx.x)
Not-Hispanic or Latino	xx (xx.x)	xx (xx.x)	xx (xx.x)
Not Reported	xx (xx.x)	xx (xx.x)	xx (xx.x)
Unknown	xx (xx.x)	xx (xx.x)	xx (xx.x)
Missing	x (xx.x)	x (xx.x)	x (xx.x)
Country, n (%)			
Canada	xx (xx.x)	xx (xx.x)	xx (xx.x)
Poland	xx (xx.x)	xx (xx.x)	xx (xx.x)
United States	xx (xx.x)	xx (xx.x)	xx (xx.x)
Woman of Childbearing Potential, n (%)			
Yes	xx (xx.x)	xx (xx.x)	xx (xx.x)
No	xx (xx.x)	xx (xx.x)	xx (xx.x)
Missing	x (xx.x)	x (xx.x)	x (xx.x)
Weight (kg)			
n	xx	xx	xx
Mean	xx.x	xx.x	xx.x
SD	xxx.xx	xxx.xx	xxx.xx
Median	xx.x	xx.x	xx.x
Q1, Q3	xx.x, xx.x	xx.x, xx.x	xx.x, xx.x
Min, Max	xx.x, xxx.x	xx.x, xxx.x	xx.x, xxx.x
Height (cm)			
n	xx	xx	xx
Mean	xxxx.x	xxxx.x	xxxx.x
SD	xxxx.xx	xxxx.xx	xxxx.xx
Median	xxxx.x	xxxx.x	xxxx.x
Q1, Q3	xxxx.x, xxxx.x	xxxx.x, xxxx.x	xxxx.x, xxxx.x
Min, Max	xxxx.x, xxxx.x	xxxx.x, xxxx.x	xxxx.x, xxxx.x
BMI (kg/m ²) [b]			
n	xx	xx	xx
Mean	xxxx.x	xxxx.x	xxxx.x
SD	xxxx.xx	xxxx.xx	xxxx.xx
Median	xxxx.x	xxxx.x	xxxx.x
Q1, Q3	xxxx.x, xxxx.x	xxxx.x, xxxx.x	xxxx.x, xxxx.x
Min, Max	xxxx.x, xxxx.x	xxxx.x, xxxx.x	xxxx.x, xxxx.x

Parameter	Imsidolimab (N=xx)	Placebo (N=xx)	All Subjects (N=xx)
-----------	-----------------------	-------------------	------------------------

N = Total number of subjects in the defined analysis set; n = Total number of subjects in the specific category.

[a] Subjects were allowed to select more than one race. Percentages can therefore add up to more than 100% in each treatment group.

[b] BMI = Weight(kg) / [Height(m)²].

Source: Listing x.x.

Report Generated by Program: <study>/<analysis>/statout/xxx.sas

Version

YYYY-MM-DD hh:mm

Notes to Programmer: Please do not display 'Missing' category with 0 counts across all columns

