1 PROTOCOL SUMMARY

1.1 SYNOPSIS

Title: A Phase 2, Randomized, Double-Blind, Placebo-Controlled Study to Evaluate the Efficacy and Safety of ANB019 in the Treatment of Subjects with Ichthyosis

Short Title: Efficacy and Safety of ANB019 in Subjects with Ichthyosis

Study Description: This is a Phase 2, multicenter, randomized, double-blind, placebo-controlled study to evaluate the efficacy, safety, and tolerability of ANB019 compared with placebo in adolescent and adult subjects with ichthyosis. This study will also characterize the pharmacokinetic (PK) profile of ANB019 and explore the immune response to ANB019 in subjects with ichthyosis.

Written informed consent will be obtained from each subject prior to initiating any study-related procedures. Subjects will also provide consent for skin biopsy collection if they wish to participate in this test.

To be eligible for the study, subjects will need to have a diagnosis of their ichthyosis subtype (as described in [Section 5.1](#)) confirmed by genetic testing.

The expected study duration per subject is approximately 44 weeks. The study will include a screening period of up to 30 days, followed by a 16-week placebo-controlled period, a 16-week open-label extension period, and an 8-week safety follow-up period.

Of note, all subjects will receive ANB019 during the open-label extension period starting on Day 113 (Week 16) visit until Day 197 (Week 28) visit. The placebo-controlled period ends on Day 113 (Week 16) visit, before study treatment administration. Therefore, the open-label extension period starts when the study treatment is administered on Day 113 (Week 16) visit.

During the placebo-controlled period, eligible subjects will be randomized (2:1) to receive either ANB019 or placebo, subcutaneously (SC) administered on 4 occasions. On Day 1, the subjects will receive a 400-mg dose of ANB019 or placebo. On Days 29, 57, and 85, the subjects will receive a 200-mg dose of ANB019 or placebo. During the open-label extension period, all subjects will receive ANB019, SC administered on 4 occasions. Subjects assigned to ANB019 during the placebo-controlled period will continue to receive a 200-mg dose of ANB019 on Days 113, 141, 169, and 197. Subjects assigned to placebo during the placebo-controlled period will receive a 400-mg dose of ANB019 on Day 113, followed by a 200-mg dose of ANB019 on Days 141, 169, and 197.

DocuSign Envelope ID: E4BE9C16-DB1E-4354-B874-2109B7254DAA

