7.1.1 TEMPORARY INTERRUPTION

Study treatment can be interrupted temporarily for any individual subject in case of an AE as per the Investigator's discretion. The Medical Monitor should be informed. Re-starting of study treatment can be done after discussion with the Medical Monitor.

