7.1.2 RE-CHALLENGE

The study treatment can be reintroduced at the next scheduled administration visit at the Investigator's discretion and after discussion with the Medical Monitor. Study treatment will be reintroduced at the 200 mg dose. In case of positive re-challenge, the study treatment should be withdrawn permanently.

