3. STUDY DESIGN

3.1 Study Design

This study is a Phase 2, multicenter, randomized, double-blind, placebo-controlled study designed to evaluate the efficacy, safety, and tolerability of imsidolimab compared with placebo in adolescent and adult subjects with ichthyosis. This study will also characterize the PK profile of imsidolimab and explore the immune response to imsidolimab in subjects with ichthyosis. Approximately 24 male and female subjects, aged 12 to 75 years, with a clinically confirmed diagnosis of ichthyosis will be enrolled in this study.

Subjects will have their ichthyosis subtype confirmed by genetic testing. In addition, the subjects will have the following characteristics at Day 1: (1) Ichthyosis Area Severity Index (IASI) total score of at least 18, (2) IASI-E (Erythema) score of at least 2 (moderate severity) in at least 1 body region and IASI-S (Scaling) score of at least 2 (moderate severity) in at least 1 body region, and (3) Body Surface Area (BSA) involved with ichthyosis of at least 50%.

The expected study duration per subject is approximately 44 weeks. The study will include a screening period of up to 30 days, followed by a 16-week placebo-controlled period, a 16-week open-label extension (OLE) period, and an 8-week safety follow-up period. During the placebo-controlled period, eligible subjects will be randomized (2:1) to receive either imsidolimab or placebo, subcutaneously (SC) administered on 4 occasions:

- 400-mg dose of imsidolimab or placebo on Day 1
- 200-mg dose of imsidolimab or placebo on Days 29, 57, and 85

During the open-label extension period, all subjects were to receive imsidolimab, SC administered on 4 occasions:

- 400-mg dose of imsidolimab on Day 113 for subjects assigned to placebo during the placebo-controlled period
- 200-mg dose of imsidolimab on Day 113 for subjects assigned to imsidolimab during the placebo-controlled period
- 200-mg dose of imsidolimab on Days 141, 169, and 197 for all subjects

However, due to study termination, no subjects reached the open-label extension period.

The overall study design is summarized and illustrated in [Figure 1](#).

[figure not shown]

Statistical Analysis Plan

Protocol No. ANB019-206
Last Revision Date: 12JAN2022

(Page 10 of 28)

Figure 1 Study Schema

Abbreviations: D, day; SC, subcutaneously; W, week

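### The rule for the treatment-discontinuation row of SAP Table 14.1.1 fixes it at 100% of treated subjects, so the row carries no information

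*SAP*

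**What the plan says.** SAP Section 7.1 lists a count of subjects who discontinued study treatment but does not define it. The only definition is the programmer note beneath the Table 14.1.1 shell in Appendix 2. The note has two clauses: "Patients who discontinued from study treatment includes 1) those who early discontinued from study", and, second, "those who did not receive all doses through Week 28". Footnote b to the row says: "The denominator for the percentages uses the number of subjects who were randomized and treated".

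The dosing schedule is a dose on Day 1, then a "200-mg dose of imsidolimab or placebo on Days 29, 57, and 85" (SAP 3.1), then extension dosing "starting on Day 113 (Week 16) visit until Day 197 (Week 28) visit" (Protocol 1.1). SAP 3.1 also states that, "due to study termination, no subjects reached the open-label extension period", and SAP 6.3.1 confirms that no study drug was given in that period.

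On missed doses, Protocol 7.1.1 says: "Study treatment can be interrupted temporarily for any individual subject in case of an AE". Protocol 7.1.2 adds: "The study treatment can be reintroduced at the next scheduled administration visit". A subject can therefore miss a dose without having discontinued.

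**The concern.** The SAP was written after the decision to terminate. It adapts much of the plan to that fact: efficacy analyses, the interim analysis, the PK analysis set and extension dose intensity are all dropped. The note to Table 14.1.1 was not adapted and still measures each subject against the full eight-dose schedule.

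A reader of a disposition table in a terminated trial wants to know how many subjects stopped treatment for reasons of their own and how many stopped only because the sponsor closed the study. A row that must equal its own denominator cannot answer that. It also sits awkwardly beside the exposure table, where the same subject may show full dose intensity for the placebo-controlled period.

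**Working it through.** The plan states no figure for this row, so there is none to reproduce. The check is whether the rule leaves the row any room to vary.

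**Inputs**
- Doses in the placebo-controlled period: Days 1, 29, 57 and 85, so 4 (SAP 3.1).
- Doses in the extension through Week 28: Days 113, 141, 169 and 197, so 4 (Protocol 1.1; SAP 3.1).
- Doses due through Week 28: 4 + 4 = 8.
- Subjects reaching, or dosed in, the extension: 0 (SAP 3.1 and 6.3.1).
- Denominator: randomized and treated subjects (Table 14.1.1, footnote b).

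**Second clause.** Let *d* be the number of doses a treated subject received through Week 28. The clause flags the subject if *d* < 8. Since *d* cannot exceed 4, it flags everyone. With *N* treated subjects in an arm, the row is 100 × *N*/*N* = 100.0%.

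The same result follows from listing dose patterns. With Day 1 given, each of Days 29, 57 and 85 given or missed, and all extension doses missed, there are 2³ = 8 patterns. All 8 are flagged, including the one with every placebo-controlled dose. On active drug that pattern is 400 + 3 × 200 = 1000 mg out of 1000 mg, or 100% dose intensity for the period.

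**First clause.** Protocol 4.5 defines completion as finishing all periods through the Week 40 visit. Nobody who never entered the extension can meet that. This clause therefore also tends to flag every treated subject, and deleting the second clause alone would probably leave the row at 100%.

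**Missed dose versus discontinuation.** Had the trial run as planned, there would be 2⁷ = 128 patterns after Day 1. All but the complete one are flagged: 127. Of these, 2⁶ − 1 = 63 include the Day 197 dose, so they show only a gap with dosing resumed. If the second clause were cut back to the four placebo-controlled doses, it would flag 7 of 8 patterns, and 2² − 1 = 3 of those include the Day 85 dose, again a gap followed by restart. The definition is therefore at odds with Protocol 7.1.1 and 7.1.2. Because the row is already 100%, no reported number changes in this study.

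**What other planned outputs show**
- Stops due to an adverse event: counted by arm in the TEAE overview table and listed in Listing 16.5.2.
- Reasons for leaving the study: the reason rows of Table 14.1.1, with early study discontinuations as denominator (footnote c), and Listing 16.1.1.
- Missed doses: doses received and dose intensity in Table 14.3.1, and the reason for a dose not given in Listing 16.4.1.
- A stop for a non-AE reason by a subject who stayed on study until closure: no tabulated count. Protocol 7.1 separates leaving treatment from leaving the study. Protocol 6.5.2 and 6.5.3 describe subjects taken off treatment because of prohibited or rescue medication, and 6.5.3 asks those it covers to complete follow-up. The study-exit reason for such a subject may simply be the sponsor's closure.

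**The case against.** The strongest reply is that little depends on this row. Every treated subject did stop before the planned last dose, so 100% is a true statement. Nearly all treated subjects should also be early study discontinuations, so the reason rows of Table 14.1.1 cover much the same people. Those rows include adverse events, disease progression, perceived lack of efficacy and termination by the sponsor. Adverse-event stops and missed doses are reported elsewhere, and the listings give dosing by subject. There is no efficacy analysis for the row to affect.

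Most of that stands, and it rules out several stronger readings that a reader might infer:
- That the table set cannot separate a subject who stopped for an adverse event from one stopped by closure. The TEAE overview and Listing 16.5.2 do so.
- That interrupted subjects distort a reported figure. They cannot move a row already at 100%.
- That the first clause misclassifies someone who finished dosing and left during follow-up. Nobody could finish dosing here.
- That the exposure table needs additions. It already covers doses received and dose intensity.

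The reply does not dispose of the gap for non-AE stops by subjects who stayed on study. It also gives no reason to print a row whose value is known before the data are read.

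**Conclusion.** Applied as written, the note makes the treatment-discontinuation row 100.0% of treated subjects in each arm and overall. It cannot distinguish stops before closure from stops caused by closure. This rests on two assumptions: that the note is programmed literally, and that the arm has at least one treated subject. The documents give no subject counts, so it is not known how many subjects a better rule would move, or whether anyone received all four placebo-controlled doses.

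The conflict with the protocol over temporary interruption is a fault of definition with no numerical effect here. The actual loss is narrow: a tabulated count of subjects who stopped dosing for a non-AE reason before the sponsor closed the study but remained on study. Severity is low. One descriptive row is affected, and no estimate, test or safety conclusion depends on it.

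**What to change.** Replace both clauses of the note and drop the Week 28 reference.

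- **Discontinued from study treatment:** dosing stopped permanently before the last dose scheduled while the subject was on study and the study was open.
- **Treatment ended by study termination:** a separate row for subjects whose dosing ended only because the study closed.

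Both rows can be derived from dates. SAP Appendix 1 takes first and last dose dates from the Dosing eCRF, and the date of study completion or discontinuation from the End of Study CRF. The note must also name the closure date to be used, which these documents do not give.

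Two cases need a stated convention. Dates alone cannot show whether a subject who missed the last dose due before closure had stopped permanently or was only interrupted. A subject who received every dose due and then left an open study falls in neither row and is covered by the study-discontinuation reasons, so a footnote should say that the two rows need not add up to the treated total.

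Give reasons for the earlier stops only if the CRF records them. The documents describe a recorded reason for leaving the study, but no separate reason for stopping treatment. No change to the exposure table is needed.

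The cost is a rewritten programmer note and one extra row.

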14.3 Safety Data Summary Tables

Extent of Exposure to Study Medication and Compliance

Table 14.3.1
Study Treatment Exposure and Compliance
Safety Analysis Set

	Imsidolimab (N=xx)	Placebo (N=xx)
Number of Doses Received		
n	xx	xx
Mean	xx.x	xx.x
SD	xx.xx	xx.xx
Median	xx.x	xx.x
Min, Max	xx, xx	xx, xx
Duration of Exposure to Study Treatment (days) [a]		
n	xx	xx
Mean	xx.x	xx.x
SD	xx.xx	xx.xx
Median	xx.x	xx.x
Min, Max	xx, xx	xx, xx
Total Dose Received (mg)		
n	xx	xx
Mean	xx.x	xx.x
SD	xx.xx	xx.xx
Median	xx.x	xx.x
Min, Max	xx, xx	xx, xx
Total Dose Expected (mg) [b]		
n	xx	xx
Mean	xx.x	xx.x
SD	xx.xx	xx.xx
Median	xx.x	xx.x
Min, Max	xx, xx	xx, xx
Dose Intensity (%) [c]		
n	xx	xx
Mean	xx.x	xx.x
SD	xx.xx	xx.xx
Median	xx.x	xx.x
Min, Max	xx, xx	xx, xx

0 - < 20%, n (%)	xx (xx.x)
20 - < 40%, n (%)	xx (xx.x)
40 - < 60%, n (%)	xx (xx.x)
60 - < 80%, n (%)	xx (xx.x)
80 - 100%, n (%)	xx (xx.x)
>100%, n (%)	xx (xx.x)
Missing	x (xx.x)

N = Total number of subjects in the defined analysis set; n = Total number of subjects in the specific category.

[a] Exposure (days) = (Date of last treatment - Date of first dose of treatment) + 1.

[b] The expected number of doses for the first dose of study treatment was 400 mg; the expected number of doses for study drug administrations after the first dose of study treatment was 200 mg.

[c] Dose intensity is defined as (Total dose received/total expected dose) x 100%.

Source: Listing xx.

Report Generated by Program: <study>/<analysis>/statout/xxx.sas

Version

YYYY-MM-DD hh:mm

Adverse Events

Table 14.3.2.1.1
Overall Summary of Treatment-Emergent Adverse Events
Safety Analysis Set

	Imsidolimab (N=xx)	Placebo (N=xx)	All Subjects (N=xx)
	n (%) [Events]	n (%) [Events]	n (%) [Events]
Subjects with at least one TEAE [a]	xx (xx.x) [xxx]	xx (xx.x) [xxx]	xx (xx.x) [xxx]
Subjects with at least one TEAE related to study treatment [b]	xx (xx.x) [xxx]	xx (xx.x) [xxx]	xx (xx.x) [xx,x]
Subjects with at least one serious TEAE	xx (xx.x) [xxx]	xx (xx.x) [xxx]	xx (xx.x) [xxx]
Subjects with at least one serious TEAE related to study treatment [b]	xx (xx.x) [xxx]	xx (xx.x) [xxx]	xx (xx.x) [xxx]
Subjects with at least one TEAE			
Leading to early treatment discontinuation	xx (xx.x) [xxx]	xx (xx.x) [xxx]	xx (xx.x) [xxx]
Leading to withdrawal from study	xx (xx.x) [xxx]	xx (xx.x) [xxx]	xx (xx.x) [xxx]
Leading to death	xx (xx.x) [xxx]	xx (xx.x) [xxx]	xx (xx.x) [xxx]
Subjects with at least one serious TEAE			
Leading to early treatment discontinuation	xx (xx.x) [xxx]	xx (xx.x) [xxx]	xx (xx.x) [xxx]
Leading to withdrawal from study	xx (xx.x) [xxx]	xx (xx.x) [xxx]	xx (xx.x) [xxx]
Leading to death	xx (xx.x) [xxx]	xx (xx.x) [xxx]	xx (xx.x) [xxx]

Subjects with at least one severe TEAE	xx (xx.x) [xxx]	xx (xx.x) [xxx]	xx (xx.x) [xxx]
Subjects with at least one severe study treatment-related TEAE [b]	xx (xx.x) [xxx]	xx (xx.x) [xxx]	xx (xx.x) [xxx]
Deaths	xx (xx.x)	xx (xx.x)	xx (xx.x)

N = Total number of subjects in the defined analysis set; n = Total number of subjects in the specific category.

[a] TEAE = Treatment-Emergent Adverse Event. An adverse event is considered treatment-emergent if the date of onset is during or after first dose of study treatment, or if the AE present at baseline that worsens in either intensity or frequency after first dose of study treatment.

[b] Related = Possibly related, related, or missing.

Source: Listing x.x.

Report Generated by Program: <study>/<analysis>/statout/xxx.sas

Version

YYYY-MM-DD hh:mm

Table 14.3.2.2.1
Summary of Subjects with Treatment-Emergent Adverse Events by Primary System Organ Class and Preferred Term
Safety Analysis Set

System Organ Class Preferred Term	Imsidolimab (N=xx)	Placebo (N=xx)	All Subjects (N=xx)
	n (%) [Events]	n (%) [Events]	n (%) [Events]
At Least One TEAE [a]	xx (xx.x) [xx]	xx (xx.x) [xx]	xx (xx.x) [xx]
System Organ Class 1	xx (xx.x) [xx]	xx (xx.x) [xx]	xx (xx.x) [xx]
Preferred Term 1	xx (xx.x) [xx]	xx (xx.x) [xx]	xx (xx.x) [xx]
Preferred Term 2	xx (xx.x) [xx]	xx (xx.x) [xx]	xx (xx.x) [xx]
System Organ Class 2	xx (xx.x) [xx]	xx (xx.x) [xx]	xx (xx.x) [xx]
Preferred Term 1	xx (xx.x) [xx]	xx (xx.x) [xx]	xx (xx.x) [xx]
Preferred Term 2	xx (xx.x) [xx]	xx (xx.x) [xx]	xx (xx.x) [xx]
Etc...			

N = Total number of subjects in the defined analysis set; n = Total number of subjects in the specific category.
MedDRA Version xx.x was used to code adverse events.

[a] TEAE = Treatment-Emergent Adverse Event. An adverse event is considered treatment-emergent if the date of onset is during or after first dose of study treatment, or if the AE present at baseline that worsens in either intensity or frequency after first dose of study treatment. AEs started on or after dosing on the Week 16 visit will not be considered as TEAEs in placebo-controlled period.

Source: Listing xx.

Report Generated by Program: <study>/<analysis>/statout/xxx.sas Version: YYYY-MM-DD hh:mm

Notes to Programmers:

Sort System Organ Class and Preferred Term by descending frequency of subjects, then by number of events for All Subjects column, and then in alphabetical order

Table 14.3.3.1
Shift Table for Laboratory Hematology Data
Safety Analysis Set

Parameter 1 (unit)

		Imsidolimab (N=xx) Baseline				Placebo (N=xx) Baseline				All Subjects (N = xx) Baseline			
Visit	Normal Range	Low	Normal	High	Missing	Low	Normal	High	Missing	Low	Normal	High	Missing
		x (xx.x)	x (xx.x)	x (xx.x)	x (xx.x)	x (xx.x)	x (xx.x)	x (xx.x)	x (xx.x)	x (xx.x)	x (xx.x)	x (xx.x)	x (xx.x)
Week 1	Low	x (xx.x)	x (xx.x)	x (xx.x)	x (xx.x)	x (xx.x)	x (xx.x)	x (xx.x)	x (xx.x)	x (xx.x)	x (xx.x)	x (xx.x)	x (xx.x)
	Normal	x (xx.x)	x (xx.x)	x (xx.x)	x (xx.x)	x (xx.x)	x (xx.x)	x (xx.x)	x (xx.x)	x (xx.x)	x (xx.x)	x (xx.x)	x (xx.x)
	High	x (xx.x)	x (xx.x)	x (xx.x)	x (xx.x)	x (xx.x)	x (xx.x)	x (xx.x)	x (xx.x)	x (xx.x)	x (xx.x)	x (xx.x)	x (xx.x)
	Missing	x (xx.x)	x (xx.x)	x (xx.x)	x (xx.x)	x (xx.x)	x (xx.x)	x (xx.x)	x (xx.x)	x (xx.x)	x (xx.x)	x (xx.x)	x (xx.x)
Week 4	Low	x (xx.x)	x (xx.x)	x (xx.x)	x (xx.x)	x (xx.x)	x (xx.x)	x (xx.x)	x (xx.x)	x (xx.x)	x (xx.x)	x (xx.x)	x (xx.x)
	Normal	x (xx.x)	x (xx.x)	x (xx.x)	x (xx.x)	x (xx.x)	x (xx.x)	x (xx.x)	x (xx.x)	x (xx.x)	x (xx.x)	x (xx.x)	x (xx.x)
	High	x (xx.x)	x (xx.x)	x (xx.x)	x (xx.x)	x (xx.x)	x (xx.x)	x (xx.x)	x (xx.x)	x (xx.x)	x (xx.x)	x (xx.x)	x (xx.x)
	Missing	x (xx.x)	x (xx.x)	x (xx.x)	x (xx.x)	x (xx.x)	x (xx.x)	x (xx.x)	x (xx.x)	x (xx.x)	x (xx.x)	x (xx.x)	x (xx.x)

<Repeat for Week 8, 12, 16, 20, 24, 28, 32, 36, and 40>

N = Total number of subjects in the defined analysis set; n = Total number of subjects in the specific category.

By study design, patients might receive different study treatments during placebo-controlled period and extension period. The first study treatment in extension period is scheduled at Week 16.

Low and High are defined as out of normal lower range and upper range respectively.

Source: Listing x.x.

Report Generated by Program: <study>/<analysis>/statout/xxx.sas

Version

YYYY-MM-DD hh:mm

Notes to Programmer: Repeat for all remaining post-baseline scheduled visits up to Week 40 Repeat for each laboratory test required within Hematology at the beginning of each page

Table 14.3.3.2
Shift Table for Laboratory Biochemistry Data
Safety Analysis Set

Notes to Programmer: Repeat format of [Table 14 5 3 4](#) for biochemistry

Table 14.3.3.3
Shift Table for Urinalysis Data
Safety Analysis Set

Notes to Programmer: Repeat format of [Table 14 5 3 4](#) for urinalysis

16. Subject Data Listings

Listing 16.1.1
Subject Disposition
All Subjects Screened

Subject ID	Age(yrs)/ Sex/Race	Erythema Severity	Treatment Assigned	Date of Informed Consent/ Date of Screening	Randomized? [a]	Date of Study Completion/ (Study Day) [b]	Discontinuation Reason	Study Completion Status	ITT/Safety Analysis Set
xxxxxx	xx/M/x	xxxxxx		YYYY-MM-DD (xx)	Yes	YYYY-MM-DD (xx)		Completed	Yes/Yes
xxxxxx	xx/F/x	xxxxxx		YYYY-MM-DD (xx)	Yes	YYYY-MM-DD (xx)	Early Terminated Lost to Follow-up		Xxx/xxx
xxxxxx	xx/M/x	xxxxxxxx		YYYY-MM-DD (xx)	Yes	YYYY-MM-DD (xx)	Early Terminated Withdrawal of Consent		Xxx/xxx
xxxxxx	xx/M/x	xxxxxx		YYYY-MM-DD (xx)	No (NA)	YYYY-MM-DD (xx)	Screen Failure Inclusion/Exclusion Criteria		No/No

NA = Not applicable.

Age is the age at the time of Informed Consent.

Sex: F = Female, M = Male.

Race: B=Black or African American, W=White, NHPI=Native Hawaiian or other Pacific Islander, AIAN=American Indian or Alaska Native,

A=Asian, O=Other, M=Multi-Race.

[a] Study Day of randomization = date of randomization - first dose of study treatment + 1.

[b] For subjects not randomized, Study Day is the last visit date - date of Screening Visit + 1; For treated subjects, Study Day is date of study completion or discontinuation on the 'End of Study' CRF - date of first dose of study treatment + 1.

Source: xxxxxxx.sas7bdat

Report Generated by Program: <study>/<analysis>/statout/xxx.sas

Version

YYYY-MM-DD hh:mm

Notes to Programmer: Sort by Subject ID. If Race is Other ("O") or Multi-Race ("M"), concatenate the specified race after 'O' or 'M' within parenthesis, e.g., "O: xxxxxx", "M: xxxxxx".

Listing 16.1.2
Treatment Assignment and Duration of Treatment
ITT Analysis Set

Subject ID	Age (yrs) / Sex/ Race	Randomization Date	Erythema Severity	Randomized Treatment	Actual Treatment	Start Treatment Day and time (24 hr clock)	End Treatment Day and time (24 hr clock)
xxxxxx	xx/M/x	YYYY-MM-DD	Moderate	xxxxxxxxxx	xxxxxxxxxx	YYYY-MM-DD hh:mm	YYYY-MM-DD hh:mm
xxxxxx	xx/F/x	YYYY-MM-DD	Moderate	xxxxxxxxxx	xxxxxxxxxx	YYYY-MM-DD hh:mm	YYYY-MM-DD hh:mm
xxxxxx	xx/M/x	YYYY-MM-DD	Severe	xxxxxxxxxx	xxxxxxxxxx	YYYY-MM-DD hh:mm	YYYY-MM-DD hh:mm

Age is the age at the time of Informed Consent.

Sex: F=Female, M=Male.

Race: B=Black or African American, W=White, NHPI=Native Hawaiian or other Pacific Islander, AIAN=American Indian or Alaska Native, A=Asian, O=Other, M=Multi-Race.

Source: xxxxxxxx.sas7bdat

Report Generated by Program: <study>/<analysis>/statout/xxx.sas

Version

YYYY-MM-DD hh:mm

Notes to Programmer: Sort by Subject ID. If Race is Other ("O") or Multi-Race ("M"), concatenate the specified race after 'O' or 'M' within parenthesis, e.g., "O: xxxxxx", "M: xxxxxx".

Listing 16.1.3
Protocol Deviations
ITT Analysis Set

Subject ID	Treatment Group	Erythema Severity	Date of Deviation Occurred	Deviation Category	Protocol Deviation Specifications
xxxxxx	Imsidolimab	xxxxxxxx	YYYY-MM-DD	xxxxxx	xxxxxxxxxxxxxxxxxxxxxxxx
xxxxxx	Placebo	xxxxxxxxxx	YYYY-MM-DD	xxxxxx	xxxxxxxxxxxxxxxxxxxxxxxx
xxxxxx	xxxxxx		YYYY-MM-DD	xxxxxx	xxxxxxxxxxxxxxxxxxxxxxxx

Source: xxxxxxxx.sas7bdat

Report Generated by Program: <study>/<analysis>/statout/xxx.sas

Version

YYYY-MM-DD hh:mm

Listing 16.2.1
Demographics

ITT Analysis Set

Subject ID	Treatment Group	Age (yrs) / Sex/Race	Erythema Severity	Ethnicity	Country	Childbearing Potential?	Height (cm)	Weight (kg)	BMI (kg/m ²)
xxxxxx	Imsidolimab	xx/F/x	xxxxxxx	xxxxxx	xxxxx	No	xxx	xxx.x	xx.xx

Age is the age at the time of Informed Consent.

Sex: F = Female, M = Male.

Race: B=Black or African American, W=White, NHPI=Native Hawaiian or other Pacific Islander, AIAN=American Indian or Alaska Native, A=Asian, O=Other, M=Multi-Race.

BMI = Body Mass Index = Height(kg)/Weight(m)².

Source: xxxxxxxx.sas7bdat

Report Generated by Program: <study>/<analysis>/statout/xxx.sas

Version

YYYY-MM-DD hh:mm

Notes to Programmer: Sort by Subject ID. If Race is Other ("O") or Multi-Race ("M"), concatenate the specified race after 'O' or 'M' within parenthesis, e.g., "O: xxxxxx", "M: xxxxxx".

Listing 16.2.2
Baseline Disease Characteristics
ITT Analysis Set

Subject ID	Treatment Group	BSA affected (%)	Ichthyosis Subtype	IASI				DLQI/CDLQI	Pruritus	Pain	iQoL-	TEWL	PGI-S
				Erythema	Scaling	Total	NASA						
xxxxxx	Imsidolimab	xx.x	xxxxxxxxxx	xx	xx	xxx	xx	xx	-/xx	x/x	x/x	x	x

Age is the age at the time of Informed Consent.

Sex: F = Female, M = Male.

Race: B=Black or African American, W=White, NHPI=Native Hawaiian or other Pacific Islander, AIAN=American Indian or Alaska Native,

A=Asian, O=Other, M=Multi-Race.

NASA = Netherton Area and Severity Assessment; IGA = Investigator global assessment; DLQI = Dermatology Life Quality Index; CDLQI = Children's Dermatology Life Quality Index; TEWL = Transepidermal water loss.

Source: xxxxxxx.sas7bdat

Report Generated by Program: <study>/<analysis>/statout/xxx.sas

Version

YYYY-MM-DD hh:mm

Listing 16.2.3
Medical History
ITT Analysis Set

Subject ID	Treatment Group	Age(yrs) / Sex/ Race	Erythema Severity	System Organ Class	Diagnosis/ (Preferred Term)	Start Date (Start Day)	[a]	Still Present?	End Date (End Day)
xxxxxx	Imsidolimab	xx/M/x	xxxxxxxxxxxx	xxxxxxxx	xxxxxx/ (xxxx)	YYYY-MM-DD (-xxx)	No	YYYY-MM-DD (-xxx)	
				xxxxxxxx	xxxxx/ (xxxx)	YYYY-MM-DD (-xxx)	No	YYYY-MM-DD (-xxx)	
xxxxxx	Placebo	xx/F/x	xxxxxxxxxxxxxxxxxxxxxx	xxxxxxxxxxxx	xxxxxx/ (xxxx)	YYYY-MM-DD (-xxx)	No	YYYY-MM-DD (-xxx)	
				xxxxxxxx	xxxxx/ (xxxx)	YYYY-MM-DD (-xxx)	Yes		

Age is the age at the time of Informed Consent.

Sex: F = Female, M = Male.

Race: B = Black or African American, W = White, NHPI = Native Hawaiian or other Pacific Islander, AIAN = American Indian or Alaska Native, A = Asian, O = Other, M = Multi-Race.

[a] Start Day = Start date of condition - date of the first dose of study treatment. Missing day is imputed as 1st of the month. Missing month is imputed as June.

[b] End Day = End date of condition - date of the first dose of study treatment. Missing day is imputed as 30th of the month. Missing month is imputed as June.

MedDRA version xx.x.

Source: xxxxxxx.sas7bdat

Report Generated by Program: <study>/<analysis>/statout/xxx.sas

Version

YYYY-MM-DD hh:mm

Notes to Programmer: Sort by Subject ID and Start Day. If Race is Other ("O") or Multi-Race ("M"), concatenate the specified race after 'O' or 'M' within parenthesis, e.g., "O: xxxxxxx", "M: xxxxxxx".

Listing 16.2.4 1
Prior Medications
Safety Analysis Set

Subject ID	Treatment Group	Age (yrs) / Sex / Race	Erythema	Medication (Preferred Name)	Dose / Unit / Frequency	Route / Indication	Start Date [a]	End Date [a]	Duration (Days) [b]
xxxxx	Imsidolimab	xx/M/x	xxxxxxxxxx	xxxxxxxxxxxx (xxxxxx)	90/ MCG / IH / PRN	COPD	YYYY- MM-DD (-xx)	YYYY- MM-DD (-xx)	No xxx
xxxxx	Placebo	xx/F/x	xxxxxxxxxxxxxx	xxxxxxxxxxxx (xxxxxx)	90/ MCG / IH / PRN	COPD Exacerbation	YYYY- MM-DD (-xx)	YYYY- MM-DD (-xx)	No xxx

Age is the age at the time of Informed Consent.

Sex: F = Female, M = Male.

Race: B = Black or African American, W = White, NHPI = Native Hawaiian or other Pacific Islander, AIAN = American Indian or Alaska Native, A = Asian, O = Other, M = Multi-Race.

Prior medication is any medication stopped prior to the first dose of study treatment.

[a] A negative number for study day denotes the number of days prior to the start of study treatment. Otherwise, study day is date of interest - date of the first dose of study treatment + 1.

[b] Number of days on rescue medication = End date of rescue medication - start date of rescue medication + 1.

WHO Drug Version xxxx.

Source: xxxxxxx.sas7bdat

Report Generated by Program: <study>/<analysis>/statout/xxx.sas

Version YYYY-MM-DD hh:mm

Notes to Programmer: Sort by Subject ID, Preferred Name, and Start Date of medication If Race is Other ("O") or Multi-Race ("M"), concatenate the specified race after 'O' or 'M' within parenthesis, e.g., "O: xxxxxx", "M: xxxxxx".

Listing 16.2.4 2
Concomitant Medications
Safety Analysis Set

*Notes to Programmer: Follow same format as [listing 14 2 4 1](#) Sort by Subject ID, Preferred Name, and Start Date of medication
If Race is Other ("O") or Multi-Race ("M"), concatenate the specified race after 'O' or 'M' within parenthesis, e.g., "O: xxxxxx", "M: xxxxxx".*

In footnote, remove definition for prior medication, and add below:

Concomitant medication is any medication continued to be taken at the time of the first dose or started after the first dose of study treatment Also, add "Pxx = Days after last dose " At the then of footnote [a]

Listing 16.2.4.3
Emollient Use, Bath and Shower (eDiary)
Safety Analysis Set

Subject ID	Treatment Group	Age (yrs) / Sex/Race	Erythema Severity	Collection Date (Day)	eDiary Entered	Bath/ Shower Time	Duration (min)	Additive Used	Emollient Type	Emollient Frequency
xxxxx	Imsidolimab	xx/M/x	xxxxxxxxxx	YYYY-MM-DD (-xx)	Yes	Hh:ss	xx	xxxxxxxxxx xxx	xxxxxxxxxx	xxxxxxxxxx
xxxxx	Placebo	xx/F/x	xxxxxxxxxx xxx	YYYY-MM-DD (-xx)	Yes	Hh:ss	xx		xxxxxxxxxx	xxxxxxxxxx

Age is the age at the time of Informed Consent.

Sex: F = Female, M = Male.

Race: B = Black or African American, W = White, NHPI = Native Hawaiian or other Pacific Islander, AIAN = American Indian or Alaska Native, A = Asian, O = Other, M = Multi-Race.

Source: xxxxxxx.sas7bdat

Report Generated by Program: <study>/<analysis>/statout/xxx.sas

Version

YYYY-MM-DD hh:mm

Note: Placeholder, mock shell to be added when data becomes available

Listing 16.2.5
Rescue Medications
Safety Analysis Set

Subject ID	Treatment Group	Age (yrs) / Sex / Race	Erythema Severity	Medication			Start Date [a]	End Date [a]	Duration (Days)
				Verbatim (Preferred Name)	Dose / Unit / Term	Route / Frequency	Indication	Continuing [b]	
xxxxx	Imsidolimab	xx/M/x	xxxxxxxxxxxx	xxxxxxxxxx (xxxxxx)	90 / MCG / IH / PRN	COPD	YYYY-MM-DD (-xx)	YYYY-MM-DD (Pxx)	No xxx
xxxxx	Placebo	xx/F/x	xxxxxxxxxx	xxxxxxxxxx (xxxxxx)	90 / MCG / IH / PRN	COPD Exacerbation	YYYY-MM-DD (-xx)	YYYY-MM-DD (-xx)	No xxx

Age is the age at the time of Informed Consent.

Sex: F = Female, M = Male.

Race: B = Black or African American, W = White, NHPI = Native Hawaiian or other Pacific Islander, AIAN = American Indian or Alaska Native, A = Asian, O = Other, M = Multi-Race.

Rescue medication is defined as a treatment, other than emollient, taken to control intolerable symptoms of ichthyosis.

[a] A negative number for study day denotes the number of days prior to the start of study treatment. Otherwise, study day is date of interest - date of the first dose of study treatment + 1. Fxx = Days after last dose.

[b] Number of days on rescue medication = End date of rescue medication - start date of rescue medication + 1.

MedDRA version xx.x.

Source: xxxxxxx.sas7bdat

Report Generated by Program: <study>/<analysis>/statout/xxx.sas

Version

YYYY-MM-DD hh:mm

Notes to Programmer: Sort by Subject ID, Preferred Name, and Start Date of medication If Race is Other ("O") or Multi-Race ("M"), concatenate the specified race after 'O' or 'M' within parenthesis, e.g., "O: xxxxxx", "M: xxxxxx".

Listing 16.3.1 1
Ichthyosis Area Severity Index (IASI) - Erythema
ITT Analysis Set

Subject ID	Treatment Group	Age (yrs) / Erythema Sex/Race	Severity	Visit	Date of Assessment (Study Day)	Time of Assessment [a]	IASI- E	Erythema			Body Region
								Body Region	Total Extent of Body Region	Percentage of Involvement (%)	
xxxxx	Imsidolimab	xx/M/x	xxxxxxxxxx	Screening	YYYY-MM-DD (-xx)	hh:mm	xx	Head and Neck	0.1	xx	xx
								Upper Limbs	0.2	xx	xx
								Trunk	0.3	xx	xx
								Lower Limbs	0.4	xx	xx
	Week 0				YYYY-MM-DD (-xx)	hh:mm	xx	Head and Neck	0.1	xx	xx
								Upper Limbs	0.2	xx	xx
								Trunk	0.3	xx	xx
								Lower Limbs	0.4	xx	xx
	Week x				YYYY-MM-DD (-xx)	hh:mm	xx	Head and Neck	0.1	xx	xx
								...			

Age is the age at the time of Informed Consent.

Sex: F = Female, M = Male.

Race: B = Black or African American, W = White, NHPI = Native Hawaiian or other Pacific Islander, AIAN = American Indian or Alaska Native, A = Asian, O = Other, M = Multi-Race.

